6. Subjects currently receiving systemic corticosteroids, inhaled corticosteroids, proton pump inhibitors (PPIs), leukotriene receptor antagonists (eg, montelukast), or mast cell stabilizers (eg, cromolyn sodium) for indications of EGE or other than EGE, or medium potency topical corticosteroids (eg, mometasone furoate cream or lotion) for dermatologic conditions, must maintain stable doses/regimens for at least 4 weeks prior to the first Screening Visit and regimens must remain stable throughout the duration of the study except for systemic corticosteroids (the dose/regimen of systemic corticosteroids must remain stable for the 16 weeks of the Induction Phase). If recently discontinued, the medication must have been discontinued at least 4 weeks prior to the first Screening Visit.
7. Female subjects of childbearing potential must agree to practice a highly effective method of contraception. Highly effective methods of contraception are those that alone or in combination result in a failure rate of a Pearl index of less than 1% per year when used consistently and correctly.

An FCBP is a female who: 1) has achieved menarche at some point; and 2) has not undergone

a hysterectomy, bilateral oophorectomy, or bilateral salpingectomy; or 3) has not been naturally postmenopausal (amenorrhea following cancer therapy does not rule out childbearing potential) for at least 24 consecutive months (ie, has had menses at any time in the preceding 24 consecutive months). An FCBP must follow the criteria below:

- a. Have 2 negative pregnancy tests as verified by the investigator prior to starting study therapy. She must agree to ongoing pregnancy testing during the course of the study and through the Final 16-week Safety Follow-up Visit. This applies even if the subject practices true abstinence\* from heterosexual contact.
- b. Either commit to true abstinence\* from heterosexual contact (which must be reviewed on a monthly basis and source documented) or agree to use, and be able to comply with, highly effective contraception without interruption throughout the study and for 5 months after the last dose of IP. Acceptable methods of birth control in this study are the following (birth control must be effective by the time the FCBP subject is randomized into the study [eg, hormonal contraception should be initiated at least 28 days before randomization]):

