## **7.3 Method of Treatment Assignment**

### **7.3.1 The Induction Phase and the Maintenance Phase**

Subjects enrolled in the Induction Phase will be centrally randomized on Day 1 after all screening and baseline assessments have been completed and the investigator has verified that the subject is eligible per the inclusion ([Section 4.2](#)) and exclusion criteria ([Section 4.3](#)). Subjects will be randomized 2:1 to receive active CC-93538 treatment (360 mg SC weekly for 16 weeks) or matching placebo for 16 weeks. Treatment assignment at baseline will be stratified by (with/without) concomitant use of corticosteroid treatment at baseline (up to 10 mg/day as the equivalent of prednisone) to ensure an equal balance in the treatment arms. Randomization will be performed through the Interactive Web Response System (IWRS) system.

Subjects enrolled in the Maintenance Phase will be centrally re-randomized on Week 16 (the completion of Induction Phase). Subjects who randomized to receive CC-93538 360 mg SC once weekly in the Induction Phase will be re-randomized 1:1 to receive active CC-93538 treatment (360 mg SC once weekly or 360 mg SC once every other week), and subjects who randomized to receive matching placebo in the Induction Phase will continue placebo. Re-randomization will also be performed through the IWRS system.

Treatment groups are described in [Section 7.2](#). The treatment each subject will receive will not be disclosed to the investigator, study center personnel, subject, Sponsor, or their representatives. The treatment codes will be held according to the IWRS. Further instructions will be provided in a separate IWRS manual.

The study blind should be maintained for persons responsible for the ongoing conduct of the study (after all subjects have completed the Week 48 assessments for endpoint analysis). Blinded persons may include but are not limited to: Clinical Research Physician (also referred to as Clinical Trial Physician), Clinical Research Scientist, Clinical Trial Manager, Study Statistician, Data Manager, Programmers, and Clinical Research Associates. For details of the emergency procedure for unblinding of individual subjects, see [Section 11.4](#).

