## **9 STATISTICAL CONSIDERATIONS**

### **9.1 Overview**

This is a Phase 3, multicenter, randomized, double-blind, placebo-controlled induction and maintenance study to assess the efficacy and safety of CC-93538 in adult and adolescent subjects with EGE. The study will incorporate a 16-week Induction Phase followed by a 32-week Maintenance Phase and an OLE Phase. Subjects will be randomized according to the following stratification factor: concomitant steroid use (yes or no). An independent DMC will be used to review the safety data regularly during the course of the study.

A primary database lock will be performed when all randomized subjects in this study have completed Week 48 of the Maintenance Phase or discontinued the study, including all Safety Follow-up Period data available to date. Analyses in the primary clinical study report (CSR) will be based on this database.

Analysis details not explained in the statistical section of the protocol will be provided in the Statistical Analysis Plan (SAP).

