#### **9.6.1.2 Changes in Mean Number of Peak eos Count from Baseline to Week 16 (Induction Phase)**

The primary analysis will be conducted on the ITT population based on an analysis of covariance (ANCOVA) model with treatment group, concomitant steroid use (yes or no), and baseline eos count included in the model. The comparison between CC-93538 360 mg SC once weekly and placebo for change in number of peak eos count from baseline at Week 16 will be made using the difference in least squares mean (LSM) at a 5% 2-sided significance level. Point estimates for the mean difference between the two treatment groups using the LS mean changes and corresponding 95% Wald CI will be reported. In addition, LSMs (standard error [SE]), arithmetic means (SD), and arithmetic mean changes (SD) will be summarized by treatment group.

Missing data will be handled using a multiple imputation (MI) approach under a missing at random (MAR) assumption.

Sensitivity analyses will be performed to support the primary analysis and provide additional insights to understand the treatment effect. For the primary estimand analysis, robustness due to missing data MI under MAR assumption will be explored using tipping point analysis ([Yan, 2009](#); [Campbell, 2011](#); [Yuan, 2014](#)). In considering the ICEs of study interest (ie, ICE number 2, use of rescue therapy/prohibited medication, and ICE number 3, treatment discontinuation followed by use of rescue therapy/prohibited medication), an analysis using the hypothetical estimand strategy for change in eos count at Week 16 will be conducted.

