## **9.6.2 Subgroup Analyses**

To assess whether the treatment effect is consistent across various groups, subgroup analyses will be performed for the primary endpoint at Week 16. Treatment differences and 2-sided 95% CIs

will be provided for each subgroup listed below. Forest plots for the treatment differences by subgroup will also be provided.

1. Concomitant steroid use (yes versus no)
2. Prior history of corticosteroid use for the treatment of EGE (yes versus no)
3. Age group (adolescents [12 to 17 years] versus adults [ $\geq 18$  years], non-elderly adults [ $< 65$  years] versus elderly adults [ $\geq 65$  years]).  
For EGID Severity Score, adolescents is set as 12 to 19 years
4. Sex (female versus male)

If there are not enough subjects within a subgroup enabling a valid statistical inference, the corresponding subgroup analyses will not be performed, and summary statistics will be provided instead.

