### **9.6.3 Analysis of Secondary Efficacy Endpoints**

#### **9.6.3.1 Analyses Methods**

##### Continuous variables:

- Changes in mean number of peak eos count per hpf from baseline to Week 48
- Changes from baseline in each of 5 domain scores of the Izumo Scale (Weeks 14, 16, 32, and 48)
- Changes from baseline in total score of EGID Severity Score (Weeks 16, 32, and 48)
- Percent changes in mean number of peak eos per hpf in GI biopsies from baseline (Weeks 16 and 48)
- The time until concomitant corticosteroid treatment to zero (and continued by Week 48) (from Week 16 through Week 48)

The analysis for continuous variables of the secondary endpoints will be conducted on the ITT population using the ANCOVA model with treatment group (CC-93538 360 mg SC once weekly, CC-93538 360 mg SC once every other week, and placebo), prior steroid use (yes or no), and baseline values included in the model. Point estimates for the mean difference between the treatment groups using the LS mean changes and corresponding 95% Wald CI will be reported. The transition from the Maintenance Phase to the OLE Phase will be treated as ICE. Missing data and ICEs will be handled via the same strategy as for the primary analysis.

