##### Dichotomous variables:

- The proportion of responders defined as subjects who achieve both clinical and histologic response (Weeks 16 and 48):
  - Clinical response is defined as the proportion of subjects achieve  $< 4/15$  in all Symptoms of Interest (Gastric Pain Symptoms domain, Stomach Heaviness Symptoms domain, and Diarrhea Symptoms domain) of the Izumo Scale
  - Histologic response is defined as a  $> 75\%$  reduction of peak gastric and/or duodenal eos count from baseline

- The proportion of subjects achieving eosinophilic histologic response defined as a > 75% reduction of peak gastric and/or duodenal eos count from baseline (Weeks 16 and 48)
- The proportion of subjects who achieve < 4/15 in all Symptoms of Interest (Gastric Pain Symptoms domain, Stomach Heaviness Symptoms domain, and Diarrhea Symptoms domain) of the Izumo Scale (Weeks 14 to 16, 30 to 32, and 46 to 48)
- The proportion of subjects for whom the dose of concomitant steroids is reduced to zero (Weeks 24, 32, 40, and 48)

The analysis of the response endpoint will be conducted on the ITT population using the Cochran-Mantel-Haenszel (CMH) test stratified by concomitant corticosteroid treatment at baseline (yes or no). In case the Mantel-Fleiss criterion is not met, the Fisher's exact test will be performed instead of the CMH test. For treatment comparison between a CC-93538 dose and placebo, the 2-sided 95% stratified Newcombe CI ([Yan, 2010](#)) for the difference in proportions using the CMH weights will be provided. Missing data and any observed data after rescue therapy/prohibited medication which may impact the efficacy assessment will be set as non-responders.

Time to event data:

- The time to event of EGE flare (Through Week 48)
- The time to event of use of rescue therapy (Through Week 48)
- The time until concomitant corticosteroid use to zero (From Week 16 through Week 48)

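### The ANCOVA for continuous secondary endpoints adjusts for an undefined prior-steroid-use term instead of the randomisation stratum, concomitant steroid use at baseline

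*Combined protocol and SAP*

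**What the plan says.** The continuous-variables part of Section 9.6.3.1 gives one ANCOVA for all the endpoints it lists. Its terms are "treatment group (CC-93538 360 mg SC once weekly, CC-93538 360 mg SC once every other week, and placebo), prior steroid use (yes or no", plus the baseline value. Those endpoints include the five Izumo domain changes, which are key secondary.

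Elsewhere the steroid factor is a different one:

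- Section 7.3.1, on assignment: "Treatment assignment at baseline will be stratified by (with/without) concomitant use of corticosteroid treatment at baseline".
- Section 9.1, on the stratification factor: "Subjects will be randomized according to the following stratification factor: concomitant steroid use (yes or no".
- Section 9.6.1.2, the primary ANCOVA: "treatment group, concomitant steroid use (yes or no), and baseline eos count included in the model".
- Section 9.6.3.1, the CMH test for responder endpoints: "stratified by concomitant corticosteroid treatment at baseline (yes or no".

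Section 9.6.2 lists concomitant steroid use as one subgroup variable and, as a second, "Prior history of corticosteroid use for the treatment of EGE (yes versus no". The ITT definition in Section 9.2 says that a subject randomised under a misreported stratum is analysed under that stratum, which presupposes that the stratum enters the analysis.

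**The concern.** One model in the efficacy section departs from the factor used for randomisation, the primary analysis and the responder analyses, and the replacement term has no definition in Section 9. It may be a drafting slip. As written, though, two programmers could derive different variables, and under one plausible derivation the model leaves out the factor randomised on.

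What is at stake is precision and consistency. Stratifying on concomitant use helps the analysis most when the factor is in the model. If it is not, the Week 16 Izumo results are adjusted differently from the primary eosinophil result in the same subjects, and their standard errors may be somewhat larger than they need to be.

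**Working it through.** **No planned figure is involved.** The plan attaches no number to the secondary model. The primary sample size in Section 9.3 reproduces and is not touched: with difference 70, SD 70, 2:1 allocation and two-sided 0.05, a t-test has 78.5% power at 36 subjects and 81.8% at 39; 39/0.9 = 43.3, rounded up to 44 and then to 45 for 2:1.

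**Step 1. What prior could mean.**

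- *Treatment history.* Section 9.6.2 uses a history variable, and Section 8 has previous EGE treatments documented in addition to the prior and concomitant record.
- *Past year.* The adult EGID Severity Score (Appendix C) asks about steroid use for EGIDs in the past year.
- *28 days before screening.* Section 8 regards treatments used in the 28 days before the first Screening Visit, or during the study, as prior or concomitant.

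**Step 2. Who is coded differently.** Under Inclusion Criterion 6 (Section 4.2), current systemic steroid users "must maintain stable doses/regimens for at least 4 weeks prior to the first Screening Visit". It adds: "If recently discontinued, the medication must have been discontinued at least 4 weeks prior to the first Screening Visit". Section 6.2 also admits subjects with no concomitant treatment.

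- Under a history reading, a baseline user is also a prior user, but someone who stopped at least 4 weeks before screening is prior yes and concomitant no. The variables disagree for these former users.
- Under the 28-day reading, those former users fall outside the window, and the remaining prior users are essentially the baseline users. The variables nearly coincide.

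**Step 3. Size under the history reading.** The documents give no steroid shares and no variance explained, so all inputs here are assumptions:

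- pc = share on concomitant steroids = 0.5
- pp = share with prior use = 0.8
- R² = share of outcome variance explained by concomitant use, after the baseline value already in the model = 0.05, 0.10 or 0.20
- concomitant users are a subset of prior users
- prior use predicts nothing beyond concomitant use

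With nesting, the squared correlation of the two indicators is

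φ² = pc(1 − pp) / [pp(1 − pc)] = (0.5 × 0.2) / (0.8 × 0.5) = 0.25,

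and pp − pc = 0.30 of subjects are coded differently. Both models spend one degree of freedom on the covariate, so the ratio of standard errors, prior-use model to stratum model, is

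√[(1 − φ²R²) / (1 − R²)].

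| R² | Calculation | SE ratio |
|---|---|---|
| 0.05 | √(0.9875 / 0.95) | 1.020 |
| 0.10 | √(0.975 / 0.90) | 1.041 |
| 0.20 | √(0.95 / 0.80) | 1.090 |

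Over pc of 0.3, 0.5 and 0.6, pp of 0.7, 0.8 and 0.9, and the same R² values, the ratio runs from 1.009 to 1.113.

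**Step 4. Size under the 28-day reading.** As pp approaches pc, φ² approaches 1 and the ratio approaches 1. The loss is close to zero.

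**Step 5. Bias.** Either covariate is fixed before Day 1, so adjusting for it does not bias CC-93538 versus placebo.

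**Step 6. An endpoint where the stratum cannot enter.** Time to zero corticosteroid is in the continuous list, but Table 2 restricts it to subjects on concomitant treatment. Concomitant use is constant there and cannot be a covariate.

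**The case against.** The strongest reply has four parts.

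- *The two terms may mean the same thing.* With Section 8's 28-day window and Criterion 6 they nearly do. This stands: the documents do not establish that the variables differ.
- *The precision figures are assumed.* This also stands. If prior means EGE-only history, nesting is not guaranteed, because Criterion 6 allows steroids for other indications. If steroid history is itself prognostic, the loss shrinks or reverses.
- *The SAP may settle it.* Section 9.1 defers details not explained in the protocol, and the Amendment 4 log in Appendix F refers to aligning Sections 9.6.2 and 9.6.3.1 with a SAP. But the covariate is stated in the protocol, so it is not an unexplained detail.
- *Secondary p-values are nominal and the primary test is untouched.* True. This limits the consequence without removing the inconsistency.

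Two stronger readings are tempting. First, the three-level treatment factor might seem to split the active arm at Weeks 14 and 16, raising the standard error by √(1/15 + 1/15) / √(1/30 + 1/15) = 1.155, or 15.5%. That requires classing Week 16 data by a regimen assigned later. Only two arms exist up to then (Sections 3.1 and 7.2.1), the Day 1 label is the natural reading, and under it there is no loss.

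Second, active subjects who never enter Maintenance have no stated factor level at Weeks 32 and 48, and a reader might infer a biased regimen comparison. If 1 to 6 of 30 were all counted as weekly, they would form 2k/(30 + k) = 6.5% to 33.3% of that group; a 0.5 to 1 SD deficit would shift weekly versus every other week by 0.03 to 0.33 SD. Every input is constructed, and the shift is below the randomised contrast's own 95% half-width of about 0.76 to 0.85 SD. The missing level is a detail Section 9.1 leaves to the SAP, whose text is not in the supplied document.

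**Conclusion.** The wording is inconsistent and should be corrected. The continuous-secondary ANCOVA names an undefined steroid term where randomisation, the primary ANCOVA and the CMH test use concomitant use at baseline.

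The consequence depends on what prior means. Under a history reading the stratum is left out and the standard error could be about 2% to 9% larger under the assumptions in Step 3; under the 28-day reading the loss is close to zero. The CC-93538 versus placebo estimate is unbiased either way. The documents state stratification only for the Day 1 assignment, so this argument is not extended to weekly versus every other week. They do not support a claim of certain precision loss, of a weakened Week 16 comparison, or of a biased regimen comparison at Weeks 32 and 48.

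**What to change.** 1. In the continuous-variables part of Section 9.6.3.1, replace prior steroid use with concomitant steroid use at baseline, taking the stratum as randomised in line with Section 9.2.
2. Omit that term for time to zero corticosteroid, where it is constant.
3. As a clarification only, state that the Week 14 and Week 16 models use the two Day 1 arms, and check in the SAP which factor level is given at Weeks 32 and 48 to active subjects who were never re-randomised.

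The cost is protocol or SAP wording and programming. No extra data or subjects are needed, and the sample size is unchanged. The change is best made before the primary database lock.

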**Table 1: Study Objectives**

Primary Objective:
The primary objective of the study is to assess the efficacy of CC-93538 versus placebo in obtaining histologic improvement based on tissue eosinophils (eos) count at Week 16.
Secondary Objective(s)

The secondary objectives are:
 

• To assess the efficacy of CC-93538 versus placebo in reducing eosinophilic gastroenteritis (EGE)-related symptoms at Week 16

• To assess the efficacy and the persistence of effect of CC-93538 versus placebo at 48 weeks in:

– Obtaining histologic improvement based on tissue eos count in EGE

– Reducing EGE-related symptoms

• To assess the persistence of effect of CC-93538 through administration of a less frequent dosing regimen at 48 weeks in:

– Obtaining histologic improvement based on tissue eos count in EGE

– Reducing EGE-related symptoms

• To evaluate the safety and tolerability of CC-93538 including characterization of the immunogenicity profile throughout the study

• To evaluate the efficacy and the persistence of effect of CC-93538 versus placebo for 48 weeks in reducing concomitant corticosteroid use

• To evaluate the time to and frequency of EGE flare events and use of rescue therapy during the study

• To assess trough concentrations of CC-93538 in subjects with EGE

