**Table 2: Study Endpoints: Induction and Maintenance Phase Endpoints Through Week 48**

Endpoint	Name	Description	Timeframe
Primary	Eosinophil histologic response	Changes in mean number of peak eosinophils (eos) per high-power field (hpf) in gastrointestinal (GI) biopsies from baseline to Week 16	Week 16
Key Secondary	Clinical response: eosinophilic gastroenteritis (EGE) -related symptoms	
Changes from baseline in each of 5 domain scores of the Izumo Scale (APPENDIX B) from baseline
 
 
• Heartburn Symptoms domain
 
• Gastric Pain Symptoms domain
 
• Stomach Heaviness Symptoms domain
 
• Constipation Symptoms domain
 
• Diarrhea Symptoms domain
 
 
Gastric Pain Symptoms domain, Stomach Heaviness Symptoms domain, and Diarrhea Symptoms domain are Symptoms of Interest of EGE
	Weeks 16 and 48
	Clinical and histologic response composite	
The proportion of responders defined as subjects who achieve both clinical and histologic response:
 
 
• Clinical response defined as the proportion of subjects who achieve < 4/15 in each of three Symptoms of Interest (Gastric Pain Symptoms domain, Stomach Heaviness Symptoms domain, and Diarrhea Symptoms domain) scores of the Izumo Scale from baseline
 
• Histologic response defined as a > 75% reduction of peak gastric and/or duodenal eos count from baseline
 
	Weeks 16 and 48
	Safety and tolerability	Safety and tolerability evaluated by the incidence, severity and relationship to CC-93538 of adverse events (AEs), serious adverse events (SAEs), clinical laboratory abnormalities, changes in vital signs, physical examination abnormalities and the presence of anti-drug antibodies, including neutralizing antibodies when warranted	Through Week 48
Secondary	Eosinophil histologic response	Changes in mean number of peak eos per hpf in GI biopsies from baseline to Week 48	Week 48
	Eosinophil histologic response	Percent changes in mean number of peak eos per hpf in GI biopsies from baseline	Weeks 16 and 48
	Eosinophil histologic response (> 75% reduction)	The proportion of subjects achieving eosinophilic histologic response defined as a > 75% reduction of peak gastric and/or duodenal eos count from baseline, respectively	Weeks 16 and 48

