#### Intent-to-treat (ITT) Population

The ITT population will consist of all randomized subjects regardless of whether or not the subject received IP (CC-93538 or placebo).

The ITT population will be used as the primary population for all efficacy parameters. Subjects who prematurely withdraw from the trial for any reason and for whom an assessment is not performed for any reason will still be included in the ITT analyses. Subjects who received incorrect IP from what was randomized will be included in the treatment group according to the intended randomization. Subjects who were randomized with a misreported stratum will be analyzed according to their original (misreported) stratum.

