## **9.6 Efficacy Analysis**

### **9.6.1 Efficacy Analysis of the Primary Endpoint**

#### **9.6.1.1 Intercurrent Event and Analysis Strategies**

The following are the intercurrent events (ICEs) of interest:

1. Treatment discontinuation in subjects without the use of concomitant rescue therapy or prohibited medication (subjects remain in the study)
2. The use of concomitant rescue therapy or prohibited medication which may impact the efficacy assessment for CC-93538
3. Treatment discontinuation followed by rescue therapy or prohibited medication which may impact the efficacy assessment for CC-93538

For intercurrent event (ICE) number 1, all observed data will be included in the primary analysis regardless of the occurrence of the ICE according to the respective endpoint definition. For ICE numbers 2 and 3, all observed data will be included in the primary analysis.

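### The Week 48 rule for early transfer to the open-label extension can credit scores on open-label weekly drug to the placebo or every-other-week arm, and the responder rule does not name the transfer

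*Combined protocol and SAP*

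**What the plan says.** **Strategy for the continuous secondary endpoints.** Section 9.6.3.1 states "The transition from the Maintenance Phase to the OLE Phase will be treated as ICE", followed by "Missing data and ICEs will be handled via the same strategy as for the primary analysis". The list covered includes change in each of the five Izumo domain scores at Week 48, which Table 2 ranks as key secondary. The ANCOVA compares three arms: weekly, every other week and placebo.

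**What the primary strategy is.** Section 9.6.1.1 keeps observed data for its first intercurrent event (stopping treatment without rescue or prohibited medication), subject to the endpoint's definition. For the other two it says "For ICE numbers 2 and 3, all observed data will be included in the primary analysis". Section 9.6.1.2 adds "Missing data will be handled using a multiple imputation (MI) approach under a missing at random (MAR) assumption". The only analysis that sets aside data after an event is confined to events 2 and 3 and to one endpoint and time: "an analysis using the hypothetical estimand strategy for change in eos count at Week 16 will be conducted".

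**Arm attribution.** Section 9.2 analyses efficacy in all randomized subjects. Its sentence on subjects given the wrong product says that they "will be included in the treatment group according to the intended randomization".

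**Who transfers, and what they receive.** Sections 3.1.4 and 3.1.6 let a subject with a severe flare and/or sustained worsening leave Maintenance and enter the OLE; entry is offered, not required. Section 6.4.2.10 counts at least four weeks without change from baseline as worsening. All OLE subjects receive 360 mg weekly.

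**Izumo collection.** Sections 6 and 6.4.2.1 have it completed weekly, including through the first OLE year.

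**Responder rule.** For dichotomous endpoints, Section 9.6.3.1 assigns non-response to missing data and to data after rescue or prohibited medication. It does not mention OLE entry.

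**The concern.** Table 1 sets 48-week objectives of efficacy and persistence versus placebo, and separately "To assess the persistence of effect of CC-93538 through administration of a less frequent dosing regimen at 48 weeks in" histology and symptoms. Transfer is driven by the outcome: a subject leaves because symptoms are bad or have not improved. If scores taken afterwards on weekly active drug are analysed under the original assignment, the arm is partly credited with a treatment that it did not include. Subjects who transfer from the weekly arm stay on the same dose and frequency, so the distortion falls on the other two arms. If the drug works, the contrast with placebo shrinks and loss of effect on every-other-week dosing can be understated.

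The same gap touches the symptom responder endpoint. A subject who transfers for sustained worsening without rescue, and then scores below 4 in the three domains of interest on open-label drug, is not caught by the non-response rule as written.

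**Working it through.** **Step 1. Do open-label scores exist at study Week 48?** OLE week at study Week 48 = 48 − transfer week, less up to 3 weeks if the 21-day gap allowed in Section 3.1.4 is used.

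- Transfer at Week 16: 48 − 16 = 32, or 29 with the gap.
- Transfer at Week 32: 48 − 32 = 16, or 13 with the gap.
- Transfer at Week 44: 48 − 44 = 4, or 1 with the gap.

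All of these fall in OLE Year 1, so weekly Izumo scores are scheduled at that time.

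**Step 2. Which rule applies to them?** The transfer is not one of the three numbered events in Section 9.6.1.1. All three keep observed data, so it does not matter which one it is matched to. Two readings follow.

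| | Literal reading | Phase-based reading |
|---|---|---|
| Basis | Section 9.6.3.1 carries over the all-observed-data rule | Table 2 is headed "Study Endpoints: Induction and Maintenance Phase Endpoints Through Week 48"; Table 3 holds OLE endpoints; OLE visits are renumbered from OLE Day 1 |
| Izumo score at 48 weeks from Day 1 | Used, under the assigned arm | Treated as missing |
| Continuous endpoints | Mix of assigned and open-label treatment | Multiple imputation under MAR after a symptom-driven exit |
| Symptom responder | Can be a responder if there was no rescue | Non-responder, as missing |
| Stated Week 48 sensitivity analysis | None | None |

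No text maps OLE weeks to study weeks. The database-lock sentence in Section 9.1 does not say what happens to subjects who moved early to the OLE. Under MAR, the imputed values predict the course on the assigned arm. How far the worsening before exit informs them depends on the imputation model, which is not given.

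**Step 3. Arm size.** The plan's own figure reproduces. A two-sided two-sample t-test (noncentral t) with difference 70, SD 70, alpha 0.05 and 2:1 allocation gives power 0.818 at 26 + 13 = 39 and 0.785 at 24 + 12 = 36, so 39 is the smallest exact 2:1 total that reaches 80%. Then 39/0.9 = 43.3, rounded up to 44; the next multiple of 3 is 45. This gives 45 × 2/3 = 30 active and 45 × 1/3 = 15 placebo, and re-randomization gives 30/2 = 15 in each active Maintenance arm.

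**Step 4. Weight per transferring subject.** 1/15 = 6.7% of an arm. If about 10% are lost by Week 16 (the Section 9.3 assumption, taken as equal across arms), 15 × 0.9 = 13.5 and 1/13.5 = 7.4%. One extra symptom responder among 15 adds 6.7 percentage points.

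**Step 5. Total size.** If k of n subjects transfer and open-label drug changes their mean Week 48 score by d points, the arm mean moves by k × d / n. The documents give neither k nor d, so the calculation stops here.

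**The case against.** The strongest reply is the phase-based reading. A subject who transfers stops Maintenance, has an Early Termination Visit and gets a new OLE baseline. Section 9.6.1.1 also ties observed data to the endpoint's definition for its first event. On that view no Maintenance Week 48 score exists and nothing from the OLE is used. This is plausible and may be what was meant, but the document does not say so. It also leaves a symptom-driven exit to MAR imputation with no Week 48 sensitivity analysis.

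Section 9.1 defers further detail to the SAP, where visit mapping would normally sit. The supplied file contains no separate SAP text, so the statement that no mapping exists is limited to what was supplied. Section 9.6.3.1 does already state a strategy, and that strategy is the problem.

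A third reply is that setting OLE values aside and imputing them is itself MAR imputation. That stands. It is why the fix needs a tipping-point analysis that penalises transfer.

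Fourth, failures are still recorded. Any worsening is documented as a flare, so time to flare and time to rescue capture these subjects. Severe flare involves rescue by definition, so those subjects are already non-responders. The composite responder also requires histology. The responder gap is therefore confined to transfer for sustained worsening without rescue. How many subjects that covers is unclear, because Section 3.1.6 also keeps mild to moderate flares (defined by no need for rescue) in Maintenance; those sentences need reconciling.

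Fifth, dilution of the placebo contrast is conservative for an efficacy claim. That is fair for placebo, but not for a claim that less frequent dosing maintains the effect.

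**Conclusion.** The point holds as a defect in how the Week 48 analyses are specified. Read literally, the stated rule uses open-label scores under the assigned arm, which does not fit the persistence objectives. The alternative reading is not stated and is not tested by any sensitivity analysis. The responder rule omits OLE entry.

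The size is unknown. What can be said is that each transferring subject carries about 1/15 of an arm, or slightly more after Week 16 losses. The direction described assumes that the drug improves Izumo scores and that some placebo or every-other-week subjects transfer.

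Three stronger inferences are tempting and not supported:

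- That the plan will certainly count open-label scores. The phase-based reading remains open.
- That the bias can be put in points from the Izumo means in Section 6.4.2.1. Patients with and without interference with daily activities differ by 6.17 − 1.96 = 4.21 (gastric pain), 5.72 − 2.37 = 3.35 (heaviness) and 7.36 − 2.25 = 5.11 (diarrhea). These are cross-sectional differences between groups among 170 patients with gastrointestinal symptoms, not a drug effect in this disease, and any transfer count would be invented.
- That the trial's main conclusion is at risk. The Week 16 primary test is unaffected, Week 48 p-values are nominal, and flare and rescue times still record these events.

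It should be fixed because the remedy is cheap and the Week 48 Izumo change is a key secondary endpoint.

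**What to change.** Amend Section 9.6.3.1 and the SAP as follows.

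1. **Dichotomous endpoints.** Count OLE entry before the time point as non-response, alongside rescue and prohibited medication.
2. **Continuous Week 48 endpoints.** State that values after the first OLE dose are not used in the main analysis. Impute from pre-OLE data: for Izumo, the weekly and Early Termination scores (Table 5 schedules no Izumo at the flare visit). Add a tipping-point analysis that shifts the imputed values of transferred subjects in the unfavourable direction, because MAR alone does not reflect the failure.
3. **Supplementary analysis.** Keep the all-observed-data analysis in that role, with a stated mapping of OLE weeks to study weeks.
4. **Entry from Induction.** State how subjects who enter the OLE directly from Induction are handled at Week 48. They are in the ITT population, but Section 9.6.3.1 names only the transition from Maintenance.

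The cost is a few sentences and the added sensitivity and supplementary analyses, with no new data collection. The drawback is more imputed values in arms of about 15.
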